6.2.4 Safety Population

The Safety Population will be the ITT population (include all enrolled subjects).

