6.1.2 Overall Consideration

The above calculations suggest a sample size of 100 subjects who complete the study. For the drop-out rate, a conservative estimate of 20% is adopted (based on STAR3, IDE G060159, the percentage of subjects not completing study in the SAP group is 9.3%); assume 65% of subjects would wear the system most of the time. Then a total of 193 subjects needs to be recruited. In general, a number of 200 will be eligible to participate in the study, with up to 300 subjects enrolled.

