6.2 Study Populations

6.2.1. Intention to Treat (ITT) Population

The Intention to Treat (ITT) population will include all enrolled subjects.

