6.4 Safety Analysis

All site reported adverse events for enrolled subjects will be summarized. The summary will include all adverse events and adverse events by: Insulin Pump Infusion set; Insulin administration and pump use; Sensor Use; Severe Hypoglycemia; Severe Hyperglycemia; Diabetic Ketoacidosis; Adverse Device Event; Serious Adverse Event and Unanticipated Adverse Device Effect. Adverse Events by Investigator will also be provided. No formal statistical analysis will be carried out.

In addition, data will be collected for a descriptive summary of device disposition; adverse events; device performance and user acceptance. Safety analysis will include a summary of the following:

All adverse events including

- Serious Adverse Events (SAE)
- Unanticipated Adverse Device Effects (UADE)
- Incidence of Severe (clinical) Hypoglycemia
- Incidence of Severe Hyperglycemia
- Incidence of Diabetic Ketoacidosis (DKA)

Adverse Events will be stratified by

- **Age**
 - Children age 7-12 years
 - Children age 13-15 years
- **Race**
 - American Indian/Alaska Native
 - Black/African-American
 - White - anticipated maximum 80%
 - Native Hawaiian/Other Pacific Islander
 - Asian
 - Subject Refused
- **Ethnicity**
 - Hispanic/Latino
 - Non-Hispanic/Non-Latino
 - Subject Refused
- **Diabetes cohorts based on BMI percentile:**

Weight Status Category	Percentile Range	N=Minimum
Underweight	Less than the 5th percentile	2
Healthy weight	5th percentile to less than the 85th percentile	30
Overweight	85th to less than the 95th percentile	4
Obese	Equal to or greater than the 95th percentile	2

BMI Percentiles according to CDC:

http://www.cdc.gov/healthyweight/assessing/bmi/childrens_bmi/about_childrens_bmi.html

[figure not shown]
- **Gender**
 - Male
 - Female
- **Hypoglycemic awareness at Baseline Questionnaire**
 - Patients with intact hypoglycemic awareness (95% confidence interval will be provided)
 - Patients who have impaired hypoglycemic awareness (95% confidence interval will be provided)
- Frequency and average duration of hypoglycemic event (based on two weeks prior to the adverse event)

- The one-sided 95% upper confidence limit of severe adverse event incidence rate (DKA and severe hypoglycemia) will be calculated. Individual one-sided 95% confidence limit for DKA only and severe hypoglycemia only will also be provided.

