10.1 Visit 1 - Day 0: Consent and Screening

General

Eligibility:

This study is open to all individuals who meet the eligibility criteria. Subjects will be considered enrolled after they have signed the Informed Consent form. The Investigational Center will be responsible for making adequate source documentation available to the sponsor to verify subject eligibility.

General

Standard Care:

It is expected that subjects will continue to undergo their routine diabetes care as per clinic standard. During routine quarterly visits data collection for the study will be obtained by the designated staff.

General

Investigational Center staff will:

- Obtain informed consent/Accent from subject/parent/caregiver
 - Subjects 7-15 years should provide assent in addition to Informed Consent from parent/caregiver
- Assess eligibility of subjects to participate in the study
- Collect demographic information and baseline characteristics, including age, gender, race, ethnicity and medical diagnosis, duration of diabetes (Screening eCRF).
- Record concomitant medications on appropriate CRF
- Obtain blood sample(s) to complete required screening A1C test, if all eligibility criteria (excluding those involving blood test results) are met:
Note: All collected blood specimens will be sent to and tested by a NGSP certified Central Laboratory. A1C testing must follow National Glycohemoglobin Standardization Program (NGSP) standards. This A1C will be used for data analysis.
- Obtain blood samples to complete required screening tests, i.e. TSH (also T3, T4 if TSH is abnormal), Creatinine
- Perform screening labs including urine or serum pregnancy test
- Subjects may be rescreened up to a maximum of two times if they do not meet inclusion/exclusion criteria at the time of their original screening
- Register subjects in CareLink Clinical (see Investigator/Coordinator binder for details) and **upload insulin pump**
- Disburse devices and supplies (e.g., pump, transmitter, glucose sensors, Bayer meter, meter strips, ketone strips) to each study subject
- Administer the following questionnaires:
 - Hypoglycemia awareness questionnaire
 - Score of 4 or more is impaired awareness. It means that subjects with this score will be assigned to the impaired hypoglycemic awareness cohort.
 - Score of 3 or less is aware. It means that subjects with this score will be assigned to the intact hypoglycemic awareness cohort.
 - EQ-5D Youth
 - Hypoglycemia Fear Scale (HFS) – Child/Teen

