3.1.2.2 Analysis Datasets, if applicable

Intention to Treat (ITT) Population

The Intention to Treat (ITT) population will include all enrolled subjects.

Completed Case (CC) Population

The Completed Cases (CC) population is all subjects who complete the trial.

Efficacy Population

The primary analysis will be performed on the CC population. Sensitivity analysis will be performed in the ITT population with multiple imputations.

Safety Population

The safety population will be the ITT population (include all enrolled subjects).

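### Safety set counts everyone who signed consent, so screen failures who never use the device can lower a per-subject rate of DKA and severe hypoglycemia

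*Protocol*

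**What the plan says.** Four statements combine.

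- Protocol 6.2.1: "The Intention to Treat (ITT) population will include all enrolled subjects". Protocol 6.2.4: "The Safety Population will be the ITT population (include all enrolled subjects". SAP 3.1.2.2 defines both sets the same way. Neither document defines a set limited to subjects who used the device.
- Protocol 10.1: "Subjects will be considered enrolled after they have signed the Informed Consent form". Consent comes before eligibility is known, since the creatinine and TSH exclusions in 5.4 depend on blood taken after consent.
- Protocol 6.1.2: "a number of 200 will be eligible to participate in the study, with up to 300 subjects enrolled". The plan therefore expects some consented subjects to prove ineligible.
- Protocol 6.4: "All site reported adverse events for enrolled subjects will be summarized". The same section, and SAP 3.1.6, promise a one-sided 95% upper confidence limit for the incidence rate of DKA and severe hypoglycemia, combined and separately. Neither gives the denominator, says whether first or all events count, or names the interval method.

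Two further statements in Protocol 10.1 bear on the size. One is "Subjects may be rescreened up to a maximum of two times". The other is the Visit 1 list, which places device disbursement and pump training at the same visit as the screening bloods.

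**The concern.** An all-enrolled set suits the capture of events, but not the denominator of a device safety rate. A child who never uses the pump or sensor cannot have an event while using it, yet adds one to a per-subject denominator. The error runs one way: DKA and severe hypoglycemia look less frequent than they were among children who used the device, and the upper limit falls with the rate.

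These limits are the main safety quantities for which the plan specifies an interval, so their denominator should be fixed in advance. SAP 3.1.3.1 commits to reporting the number enrolled and the reasons for discontinuing, but not the number who used the device, so a reader may be able to correct the rate only in part.

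**Working it through.** **The plan's own figures.** Protocol 6.1.2 takes 100 completers, 20% drop-out and 65% wearing the system most of the time: 100 / (0.80 × 0.65) = 192.3, rounded up to 193, as stated, then set at 200 eligible. The cap of 300 enrolled is not derived from a screen-failure rate. It gives at most 300 − 200 = 100 consented but ineligible subjects.

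**Assumptions.** The documents give no expected event rate, screen-failure count or share of screen failures exposed. I take 200 eligible subjects, all exposed; N = 220, 250 or 300 enrolled; and either none or half of the screen failures exposed. For illustration, 5 exposed subjects have an event. The interval is Clopper-Pearson, also an assumption.

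**Per-subject rate.** With n exposed subjects, the cut is 1 − n/N. The one-sided 95% upper limit for x affected subjects out of m is the 0.95 quantile of Beta(x + 1, m − x).

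| Enrolled N | Exposed n | Cut in rate | Upper limit on n, x = 5 | Upper limit on N, x = 5 |
|---|---|---|---|---|
| 220 | 210 (half) | 10/220 = 4.5% | 4.94% | 4.72% |
| 250 | 225 (half) | 25/250 = 10.0% | 4.62% | 4.16% |
| 300 | 250 (half) | 50/300 = 16.7% | 4.16% | 3.47% |
| 220 | 200 (none) | 20/220 = 9.1% | 5.18% | 4.72% |
| 250 | 200 (none) | 50/250 = 20.0% | 5.18% | 4.16% |
| 300 | 200 (none) | 100/300 = 33.3% | 5.18% | 3.47% |

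**Coverage of the nominal 95% limit** for the risk in exposed subjects is the sum of Binomial(n, p) probabilities over every x whose limit, computed on N, is at least p. At an assumed p = 5%, with half exposed, it is 95%, 94% and 88% at N = 220, 250 and 300. With none exposed it is 94%, 88% and 67%, against 97% when the denominator is the 200 exposed.

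**Person-time rate.** Assume 20% of the 200 drop out at mid-year on average: 160 × 1 + 40 × 0.5 = 180 person-years. Each screen failure adds 7 to 30 days.

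- 20 screen failures add 0.38 to 1.64 person-years; the cut is 0.2% to 0.9%.
- 100 screen failures add 1.92 to 8.22 person-years; the cut is 1.1% to 4.4%.
- With 5 events the Poisson upper limit is the 0.95 chi-square quantile on 12 degrees of freedom, halved, over person-years: 10.513/180 = 5.84 per 100 person-years. In the largest case it becomes 10.513/188.22 = 5.59.

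**The case against.** The strongest reply concerns size. Consent, blood draw, device disbursement and training all fall at Visit 1, the bloods go to a central laboratory, and no later disbursement visit is listed before Day 90. A child who fails on a laboratory result could already have the pump and would rightly belong in Safety. If 80% of screen failures were exposed (assumed), the cut would be only 4/220 = 2%, 10/250 = 4% or 20/300 = 7%. This stands: the none-exposed figures are a ceiling and not an expectation.

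Second, incidence rate may mean person-time, and then the effect is small. That also stands, but the text does not settle it, and the possible effect runs from a fraction of a percent to a third.

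Third, readers would have some help. Both safety sections promise a descriptive summary of device disposition, and Table 2 of the protocol records device disbursement by eCRF. These would go some way to showing who received a device, though not who used one.

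Fourth, the coverage loss is measured against the risk in exposed subjects, a target the plan does not state, and it depends on the assumed risk: at 1%, coverage with none exposed is about 100% at 220 and 250 enrolled and 87% at 300. The coverage figures are illustrations.

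A reader might also infer that the efficacy result is compromised, because the SAP says "Sensitivity analysis will be performed in the ITT population with multiple imputations" and ITT includes screen failures. The documents do not support going that far. The primary analysis uses completers, the imputation details may lie in redacted text, and the right set for that sensitivity analysis is a separate question.

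**Conclusion.** The point holds for the safety denominator. Read as written, the two documents put consented children who never use the device into the safety set, and leave open whether the key rates are per subject or per person-time.

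The size depends on that choice and on the unknown share of screen failures exposed. The half-exposed per-subject figures (about 5%, 10% or 17%) are a reasonable middle case under an assumed share. A one-third cut or 67% coverage should not be read as the expected effect. Both need a per-subject denominator, enrolment at the cap and no exposed screen failure; the coverage figure also needs an assumed 5% risk and the assumed interval method.

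Protocol 6.4 rules out formal safety testing and sets no threshold, so neither a trial decision nor the non-inferiority conclusion changes. What suffers is the reading of the DKA and severe hypoglycemia rates. It should be fixed because the bias has one direction and the remedy is cheap.

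**What to change.** - **Protocol 6.2.4 and SAP 3.1.2.2:** define Safety as all consented subjects who use the study pump or sensor on or after consent, including any later found ineligible. Dating exposure from consent matters because exclusion 16 admits children with up to 7 days on a 530G with CGM.
- **Protocol 6.4 and SAP 3.1.6:** base the rates and upper limits on that set, state whether the denominator is subjects or person-years of device use, and list events in consented but unexposed subjects separately, so that no event is lost.
- **SAP 3.1.3.1:** report the numbers consented, eligible and exposed, using the device disbursement eCRFs and CareLink uploads.

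The cost is wording in these sections plus a first-use date for each subject. Devices supplied commercially under an early protocol version fall outside device accountability (Protocol 11.5), so for those subjects the date must come from uploads or a site record. Reported rates may become slightly less favourable.

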6.3 Analysis of Primary Endpoint

6.3.1 Primary Efficacy Analysis

A mixed effects model be used to produce the estimate and confidence interval of the overall mean change in A1C while accounting for inter-site variability. The 97.5% upper confidence interval of A1C will be calculated and compared to the 0.4% non-inferiority margin. As for endpoint analysis, the proposed mixed effects model using all A1C measurements has more power than the model only using Change in A1C from baseline to one-year visit.

$$Y_{ij} = X_{ij}\beta + B_i + B_{ij} + \epsilon_{ij}$$

where

$\mathbf{I}_j = (I_{j1}, \dots, I_{jT})'$ is the A1C measurement vector for the jth subject in the ith site;

$$\begin{bmatrix} 1 & 0 & 0 & 0 \\ 1 & 1 & 0 & 0 \\ \vdots & \vdots & \vdots & \vdots \\ 1 & 0 & 1 & 0 \\ 1 & 0 & 0 & 1 \end{bmatrix}$$

$\mathbf{C}_j = (C_{j1}, \dots, C_{jT})'$ is a the covariate vector for the jth subject in the ith site;

$$\begin{bmatrix} \beta_0 \\ \beta_1 \\ \beta_2 \\ \vdots \\ \beta_4 \end{bmatrix}$$

[figure not shown]
$\beta = \begin{bmatrix} \beta_0 \\ \beta_1 \\ \beta_2 \\ \vdots \\ \beta_4 \end{bmatrix}$ is the coefficient vector, β_0 estimate the mean A1C at baseline, β_1 estimate the mean change of A1C from baseline to one-year visit;

$\mathbf{B}_i = (b_{i1}, \dots, b_{iT})'$ is the random effect vector for the ith site;

$\mathbf{B}_j = (b_{j1}, \dots, b_{jT})'$ is the random effect vector for the jth subject in the ith site;

$\mathbf{e}_j = (e_{j1}, \dots, e_{jT})'$ is the random error term;

"The mean of baseline A1C measurement is estimated by β_0 , mean of 3-month A1C measurement estimated by $\beta_0 + \beta_1$, ..., mean of 12-month A1C measurement estimated by $\beta_0 + \beta_1 + \dots + \beta_4$, i.e., β_1 estimate the mean change of A1C from baseline to one-year visit; the 97.5% upper confidence interval of β_1 will be calculated and compared the 0.4% non-inferiority margin."

6.4 Safety Analysis

All site reported adverse events for enrolled subjects will be summarized. The summary will include all adverse events and adverse events by: Insulin Pump Infusion set; Insulin administration and pump use; Sensor Use; Severe Hypoglycemia; Severe Hyperglycemia; Diabetic Ketoacidosis; Adverse Device Event; Serious Adverse Event and Unanticipated Adverse Device Effect. Adverse Events by Investigator will also be provided. No formal statistical analysis will be carried out.

In addition, data will be collected for a descriptive summary of device disposition; adverse events; device performance and user acceptance. Safety analysis will include a summary of the following:

All adverse events including

- Serious Adverse Events (SAE)
- Unanticipated Adverse Device Effects (UADE)
- Incidence of Severe (clinical) Hypoglycemia
- Incidence of Severe Hyperglycemia
- Incidence of Diabetic Ketoacidosis (DKA)

Adverse Events will be stratified by

- **Age**
 - Children age 7-12 years
 - Children age 13-15 years
- **Race**
 - American Indian/Alaska Native
 - Black/African-American
 - White - anticipated maximum 80%
 - Native Hawaiian/Other Pacific Islander
 - Asian
 - Subject Refused
- **Ethnicity**
 - Hispanic/Latino
 - Non-Hispanic/Non-Latino
 - Subject Refused
- **Diabetes cohorts based on BMI percentile:**

Weight Status Category	Percentile Range	N=Minimum
Underweight	Less than the 5th percentile	2
Healthy weight	5th percentile to less than the 85th percentile	30
Overweight	85th to less than the 95th percentile	4
Obese	Equal to or greater than the 95th percentile	2

BMI Percentiles according to CDC:

http://www.cdc.gov/healthyweight/assessing/bmi/childrens_bmi/about_childrens_bmi.html

[figure not shown]
- **Gender**
 - Male
 - Female
- **Hypoglycemic awareness at Baseline Questionnaire**
 - Patients with intact hypoglycemic awareness (95% confidence interval will be provided)
 - Patients who have impaired hypoglycemic awareness (95% confidence interval will be provided)
- Frequency and average duration of hypoglycemic event (based on two weeks prior to the adverse event)

- The one-sided 95% upper confidence limit of severe adverse event incidence rate (DKA and severe hypoglycemia) will be calculated. Individual one-sided 95% confidence limit for DKA only and severe hypoglycemia only will also be provided.

6.5 Secondary Endpoint

The mean change in A1C from baseline to 3-month, 6-month, 9-month and 12-month will be summarized individually for each of the three baseline A1C cohorts:

- A1C less than 7.0%;
- A1C between 7.0% to 9.0;
- A1C greater than 9.0%

Re

7. Institutional Review Board

This protocol, any subsequent amendments to this protocol, the Informed Consent form, subject material and any form of subject recruitment information (e.g. advertisements) relating to this study will be approved by the responsible IRB in accordance with 21 CFR Part 56. The study will not start until IRB approval has been granted, the Sponsor has cleared the Investigational Center to begin the study, and the investigational clinical staff has been appropriately trained to conduct the study. Copies of all relevant correspondence between the Investigational Center and the IRB will be retained on-site with copies forwarded to the Sponsor for their files.

8. Subject Confidentiality

8.1 *Subject Identification*

The identity of the subjects may not be disclosed, unless required by law, to any persons not immediately involved in the study or the study procedures. All correspondence between the Investigational Center and Medtronic that refers to individual study subjects will use unique identifiers that are specific to each

subject in lieu of subject names. Furthermore, all subject names will be redacted from reports, safety updates, and source documents that are forwarded to the Medtronic.

8.2 *Subject Database Assignment*

In the Oracle Clinical database, the Investigational Centers will be identified numerically, i.e. from 01 to 25 (depending on center number). At the Screening visit, Investigational Center staff will assign each subject a sequential ID number that corresponds to a pre-defined casebook in the Oracle database.

Each case book will contain all relevant Case Report Forms for each subject. Subjects will be assigned a unique 9-digit identifier that will be structured such that the first 3 digits correspond to the study number (287), the next 3 digits correspond to the Investigational Center number, and the final 3 digits correspond to the subject number. An example of a typical subject's unique identifier is shown in the following example: The numerical sequence 287001001 translates into: Study number (287), Investigational Center number (001), Subject number (001).

All study documents, eCRFs and correspondence will use this identifier sequence in lieu of a subject's name or initials.

8.3 *Informed Consent*

Informed Consent/ Assent will be obtained in accordance with the Code of Federal Regulations (CFR) Title 21, Part 50. Prior to entry into the study the California Experimental Subject's Bill of Rights (if applicable), the IRB- and Medtronic-approved Informed Consent Form (ICF)/Assent, and the HIPAA Authorization Form will be given to each subject. Subjects/parents/caregivers will be offered the opportunity to review these documents away from the Investigational Center. Pediatric subjects 7-15 years of age should provide informed assent to participate in this research even if their parents or guardians have given permission for their participation through informed consent. A subject's participation in study procedures cannot start before the consent process has been properly executed.

9. *Investigator Responsibilities*

This study will be conducted at up to 20 Investigational Centers where all study-related activities will take place; at each center, the study will be led by a principal Investigator. Per 21 CFR 56.102, an Investigator is "an individual who actually conducts a clinical investigation (i.e., under whose immediate direction the test article is administered or dispensed to, or used involving, a subject) or, in the event of an investigation conducted by a team of individuals, is the responsible leader of that team." Specific responsibilities of the principal investigator are described in 21 CFR 812.100 and in the FDA guidance document dated October, 2009 (see Regulatory Binder).

10. Study Visits

Chart 1: Visit 1-5

[figure not shown]

Table 1: Visit Plan and Study Activities

	Visit 1 Screening	Visit 2 90 Day A1C	Visit 3 180 Day A1C	Visit 4 270 Day A1C	Visit 5 365 Day A1C End of Study
Study Activities at Site during visit	Informed Consent Eligibility Assessment Subject Demography Record Concomitant medications Screening A1C Lab Draw Administer Questionnaires Case Report Forms Distribute devices and supplies (e.g., pump, transmitter, Bayer meter, glucose sensors, meter strips, ketone strips) to each subject Dislodgement Subject Diary Study Pump Training CareLink Registration Help Line Training Case Report Forms EQ5-5DYouth questionnaire HFS Parent questionnaire HFS Child/Teen questionnaire Hypoglycemia Unawareness questionnaire Upload insulin pump Instruct subjects to use either Humalog or Novolog insulins Instruct Subjects to use the Bayer Contour Link meter for all calibrations	Adverse Event Check CareLink Upload A1C Test Case Report Forms Distribute devices and supplies (e.g., glucose sensors, meter strips, ketone strips) that need replenishing to each subject Review Sensor Dislodgement Diary Distribute Urine Ketone Test strips Remind subjects to use either Humalog or Novolog insulin Remind Subjects to use the Bayer Contour Link meter for all calibrations	Adverse Event Check CareLink Upload A1C Test Case Report Forms Distribute devices and supplies that need replenishing (e.g., glucose sensors, meter strips, ketone strips) to each subject Review Sensor dislodgement Diary Distribute Urine Ketone Test strips Remind subjects to use either Humalog or Novolog insulin Remind Subjects to use the Bayer Contour Link meter for all calibrations	Adverse Event Check CareLink Upload A1C Test Case Report Forms Distribute devices and supplies that need replenishing (e.g., glucose sensors, meter strips, ketone strips) to each subject Review Sensor dislodgement Diary Distribute Urine Ketone Test strips Remind subjects to use either Humalog or Novolog insulin Remind Subjects to use the Bayer Contour Link meter for all calibrations	Adverse Event Check CareLink Upload A1C Test Case Report Forms EQ5-5DYouth questionnaire HFS Parent questionnaire HFS Child/Teen questionnaire Hypoglycemia Unawareness questionnaire Review Sensor dislodgement Diary Return of Study Devices and supplies

	Visit 1 Screening	Visit 2 90 Day A1C	Visit 3 180 Day A1C	Visit 4 270 Day A1C	Visit 5 365 Day A1C End of Study
Study Activities at Home between visits		
Upload the Pump every 21 days
 
Change Sensors as required
 
Test urine ketones daily and enter test results into CareLink Clinical
 
Call the study doctor and his staff if you are experiencing any medical problem either related to your diabetes or unrelated to your diabetes
 
Call the Medtronic 24 Hr helpline if you have a device problem
 
Fill out a Sensor Dislodgement Diary as needed
	
Upload the Pump every 21 days
 
Change Sensors as required
 
Test urine ketones daily and enter test results into CareLink Clinical
 
Call the study doctor and his staff if you are experiencing any medical problem either related to your diabetes or unrelated to your diabetes
 
Call the Medtronic 24 Hr helpline if you have a device problem
 
Fill out a Sensor Dislodgement Diary as needed
	
Upload the Pump every 21 days
 
Change Sensors as required
 
Test urine ketones daily and enter test results into CareLink Clinical
 
Call the study doctor and his staff if you are experiencing any medical problem either related to your diabetes or unrelated to your diabetes
 
Call the Medtronic 24 Hr helpline if you have a device problem
 
Fill out a Sensor Dislodgement Diary as needed
	

